5.3.2 Slit Lamp Examination

Slit-lamp examination will be performed at all non-operative visits (pre-operative Visit 0 and post-operative Visit 1, Visit 2, Visit 3) and at any unscheduled visit.

Number and percentage of slit lamp findings will be summarized for each visit by procedure. A listing including all slit-lamp data will be provided for each visit by procedure.

5.3.3 Corneal Edema

Grade from 0 to 3 for signs of corneal edema are: 0-None, 1-Mild, 2-Moderate and 3-Severe.

Corneal edema grade will be summarized for each visit by procedure. A listing of corneal edema grade will be provided for each visit by procedure.

5.3.4 Dilated Fundus Examination

Fundus examination will be performed at pre-operative Visit 0 and post-operative Visit 3.

Number and percentage of fundus exam findings will be summarized for each visit by procedure. A listing of fundus exam findings will be provided for each visit by procedure.

5.3.5 Best Corrected Distance Visual Acuity (BCDVA)

Best corrected distance visual acuity (BCDVA) will be performed at Screening (Visit 0), Day 7 (Visit 2) and Day 90 (Visit 3) visits.

Observed and change from baseline BCDVA values will be presented descriptively. In addition, frequency and percentages of subjects who experience a pre-specified category of change in BCDVA from Baseline to last post-baseline assessment visit and maximum loss from Baseline to any post-baseline assessment visit will be presented according to the following mutually exclusive categories: <1 line loss or improvement, ≥ 1 line loss and ≥ 2 line loss.

A listing of all subjects with a ≥ 2 line in BCDVA from baseline to any post-baseline visit will be presented. For subjects who had ≥ 2 line loss at any study visit, BCDVA values at all visits will be presented. Subject listings will include the following variables: investigational procedure, subject, age, sex, race, visit, eye, baseline VA, VA at the visit and VA change from baseline.

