#### 10.1 Inclusion Criteria

- 1. Adult patients 21 years of age or older of either gender or any race.
- 2. Willing and able to consent for participation.
- 3. Willing and able to attend postoperative examinations per protocol schedule.
- 4. Patients must have a cataract in at least one eye with a Nuclear Opalescence of II-IV (via LOCS II) followed by posterior chamber IOL implantation

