### 10.2 Exclusion Criteria

- 1. Subjects whose postoperative best corrected visual potential is expected to be worse than 20/60 Snellen (0.5 effects logMAR) at the final study visit.
- 2. Planned multiple procedures, including Laser Phaco, LASIK, LRI's etc during surgery or the course of this study.
- 3. Clinically significant corneal endothelial dystrophy (eg, Fuch's dystrophy, ECD < 1500 cells/mm^2)
- 4. Patients who have severe conditions of acute or chronic diseases or illnesses that, per Investigator's clinical judgment, would increase the operative risk or confound the result of this investigation.
- 5. Small pupil size that will require mechanical dilation using iris hooks, Malyugin ring or similar devices effects.
- 6. Weaken /Broken zonules
- 7. Subjects who were enrolled in the study may not be re-enrolled for the second eye.
- 8. Untreated or uncontrolled Glaucoma

**Document:** TDOC-0050176 **Version:** 2.0; Effective; CURRENT

Status: Effective Page 31 of 75

9. Previous intraocular or corneal surgery of any kind, including any type of surgery for either refractive or therapeutic purposes.

- 10. A poorly dilating pupil or other pupil defect that prevents the iris from retracting peripherally to at least 5 mm dilation.
- 11. Current or previous usage of an alpha-1-selective adrenoceptor blocking agent or an antagonist of alpha 1A adrenoceptor (eg, Flomax® (tamsulosin hydrochloride), Hyntrin® (terazosin hydrochloride), or Cardura® (doxazosin mesylate).
- 12. Diagnosed with severe retinal disorders (eg, macular degeneration, proliferative diabetic retinopathy).
- 13. History of corneal disease (eg, herpes simplex, herpes zoster, etc).
- 14. History of retinal detachment.
- 15. Known zonular instability or zonular dehiscence (eg, Marfan's syndrome, pseudoexfoliation syndrome, etc).
- 16. Any patient currently participating in another drug or device study

**Document:** TDOC-0050176 **Version:** 2.0; Effective; CURRENT

Status: Effective Page 32 of 75

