## 12.1.2.4.4 Successful Placement of IOL in Capsular Bag

Indicate in the medical notes if IOL placement in the capsular bag was successful.

**Document:** TDOC-0050176 Version: 2.0; Effective; CURRENT

Status: Effective Page 41 of 75

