5.3.8 IOL Placement

IOL placement data is collected at operative Visit 00 (Day 0).

Numbers and percentages on eye(s) with a change from baseline in IOL position category (Tilted, Decentered) will be presented by procedure. A listing of subjects with IOL position change will be provided by procedure. The listing will include the following variables: procedure, investigator, subject, age, sex, visit, eye and amount of tilting or decentration.

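### SAP 5.3.5 calls overlapping BCDVA loss rows mutually exclusive, and SAP 5.3.8 plans a change from baseline in IOL position when IOL placement is documented at one visit only

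*SAP*

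**What the plan says.** **BCDVA.** SAP 5.3.5 schedules BCDVA at Visits 0, 2 and 3, so a baseline exists and change can be computed. Two frequency summaries are planned: change at the last post-baseline visit, and maximum loss at any post-baseline visit. Both use "mutually exclusive categories: <1 line loss or improvement, ≥ 1 line loss and ≥ 2 line loss". The section also plans a listing of the larger losses: "For subjects who had ≥ 2 line loss at any study visit, BCDVA values at all visits will be presented".

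**IOL placement.** SAP 5.3.8 opens with the collection time: "IOL placement data is collected at operative Visit 00 (Day 0"). It then plans the analysis: "Numbers and percentages on eye(s) with a change from baseline in IOL position category (Tilted, Decentered) will be presented by procedure". A listing follows: "The listing will include the following variables: procedure, investigator, subject, age, sex, visit, eye and amount of tilting or decentration".

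The schedules in protocol section 6 and the SAP appendix both mark IOL placement at Visit 00 and nowhere else. Protocol 12.1.2.4.4 says what is recorded: "Indicate in the medical notes if IOL placement in the capsular bag was successful". Inclusion criterion 4 requires "a cataract in at least one eye with a Nuclear Opalescence of II-IV (via LOCS II) followed by posterior chamber IOL implantation". Exclusion criterion 9 rules out "Previous intraocular or corneal surgery of any kind, including any type of surgery for either refractive or therapeutic purposes".

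BCDVA and IOL placement are named safety endpoints in protocol 8.4.2 and 15.7 and in SAP 5.1.

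**The concern.** In the BCDVA table, the label and the cut-points contradict each other. A programmer has to give up either the exclusivity or the literal meaning of the ≥1 line row. If exclusivity is kept, a reader of that row could take it as everyone who lost at least one line, when the larger losses sit in the row below.

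In the IOL table, a change needs two readings and the documents provide for one. Followed literally, the table is either empty or shows no changes. A table of zeros could be read as no displaced lenses when nothing was compared. Meanwhile, the outcome the protocol does ask for, whether the lens was placed in the bag, has no summary in 5.3.8.

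Left alone, someone has to settle both points at programming, possibly after seeing data by arm.

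**Working it through.** The plan gives no figure to reproduce on this point, so the check is one of logic and counting.

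**1. BCDVA rows.** Let x be lines lost, with a gain negative. The number of SAP labels that x meets is

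m(x) = [x < 1] + [x ≥ 1] + [x ≥ 2], each bracket being 1 if true and 0 if not.

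| x | SAP labels met | Labels met with rows <1; ≥1 to <2; ≥2 |
|---|---|---|
| −3 | 1 | 1 |
| 0 | 1 | 1 |
| 0.9 | 1 | 1 |
| 1 | 1 | 1 |
| 1.9 | 1 | 1 |
| 2 | 2 | 1 |
| 3 | 2 | 1 |
| 5 | 2 | 1 |

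The SAP rows cover every value but overlap for every x ≥ 2. If the labels are applied literally, the row total is N plus the number of subjects with x ≥ 2.

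The documents give no expected loss rates, so the splits below are assumptions that only show the mechanism. Each uses one arm of 53, the evaluable number per group in SAP 1.2.

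| Assumed subjects: <1 / ≥1 to <2 / ≥2 | Literal SAP rows | Row total | Percent of 53 |
|---|---|---|---|
| 53 / 0 / 0 | 53 / 0 / 0 | 53 | 100.0 |
| 50 / 2 / 1 | 50 / 3 / 1 | 54 | 101.9 |
| 48 / 3 / 2 | 48 / 5 / 2 | 55 | 103.8 |
| 45 / 4 / 4 | 45 / 8 / 4 | 57 | 107.5 |

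If exclusivity is kept instead, nobody is counted twice, but the printed label misleads. In the 48 / 3 / 2 split, the ≥1 line row would show 3 subjects (3/53 = 5.7%), although 3 + 2 = 5 (5/53 = 9.4%) lost at least one line.

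**2. IOL position.** Documented IOL placement assessments per eye, from SAP 5.3.8 and the two schedules:

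- before surgery: 0
- Visit 00: 1
- after surgery: 0

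A pre-operative value is impossible. The IOL is implanted at the study surgery (protocol 10.1, criterion 4), and earlier intraocular surgery is excluded (protocol 10.2, criterion 9). Pairs per eye are therefore 0, and across 3 × 59 = 177 planned eyes the number with a documented pair is 0.

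**3. Content of the one assessment.** Protocol 12.1.2.4.4 asks whether in-the-bag placement succeeded. The visible text defines no tilt or decentration category and no amount, although the 5.3.8 listing calls for an amount.

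**4. Other possible source.** Slit-lamp examinations take place at Visits 1, 2 and 3 for all subjects (protocol 12.1.3.4, 12.1.4.5 and 12.1.5.5). Those sections name the natural crystalline lens but not IOL position. SAP 5.3.8 does not cite them, and SAP 5.3.2 already summarises their findings by visit.

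**The case against.** **BCDVA.** The instruction that the rows are mutually exclusive can be read as governing. A careful programmer would then put a 2-line loss only in the last row, and nothing is double counted. Observed values, change from baseline and the listing of larger losses are also planned, so no safety information disappears. This is largely right: the exclusive reading is the only one that honours the instruction and keeps the last row usable. That limits the BCDVA point to a labelling error, but the printed label would still be wrong.

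**IOL.** Protocol 12.1 defers detail to the Manual of Procedures, and neither the Manual nor the eCRF is available. Tilt or decentration fields may exist there. SAP 5.3.8 does not define baseline, so Visit 00 could be the reference, with later position taken from the slit lamp. The inclusion of visit among the listing variables fits that reading. The post-operative slit-lamp text looks carried over from the pre-operative visit, since it names a lens that has been removed. Its list is not exhaustive, and new observations must be recorded. It therefore cannot show that IOL position goes unrecorded.

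Two parts of this stand. The zero count describes the documented schedule and not the database, and tilt or decentration output should depend on what the eCRF holds. The rest does not rescue the section. Tilt fields at Visit 00 alone would still give one reading, and incidental slit-lamp notes are not a planned paired assessment. Section 5.3.8 names Visit 00 as its collection time and cites no other source.

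**Conclusion.** The concern holds on both parts, at low severity.

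- **BCDVA:** every loss of 2 or more lines meets 2 of the 3 labels, and the labels are used in 2 summaries. This is a minor relabelling and rests on no assumption about event rates.
- **IOL placement:** the change table cannot be produced from the documented IOL placement data, with 0 of 177 planned eyes having a pair. This is the weightier part. It rests on the visible protocol, SAP and schedules, because the eCRF and the Manual of Procedures could not be checked.

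SAP 5.2 sets no safety hypotheses and both outputs are descriptive. The CDE and BSS comparisons, the type I error and the sample size do not depend on either.

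**What to change.** **SAP 5.3.5.** Relabel the rows *<1 line loss or improvement*, *≥1 to <2 line loss* and *≥2 line loss*. Keep the 2-line listing.

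**SAP 5.3.8.**
- Remove the change from baseline. Summarise IOL placement status as observed at Visit 00, by procedure, with n and percent (the rule SAP 5.3 already sets for categorical safety data), plus a listing.
- Report in-the-bag success as recorded under protocol 12.1.2.4.4.
- Report tilt or decentration only if the eCRF holds those fields.
- State that a displaced IOL seen later is reported through slit-lamp findings (5.3.2) or adverse events (5.3.1).

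**Cost.** Wording in two SAP subsections, with no new data collection proposed. One check comes first. Protocol 12.1.2.4.4 puts in-the-bag success in the medical notes. Protocol 14.1 calls for required examinations to be on the eCRFs, and IOL placement is a scheduled Visit 00 activity, so the item is probably captured. The sponsor should confirm this, and which IOL position fields exist, before the table is specified.

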5.3.6 Intraocular Pressure

IOP assessment is performed at all non-operative visits (pre-operative Visit 0 and post-operative Visit 1, Visit 2, Visit 3), and at any unscheduled visit.

Descriptive summaries (N, mean, median, and standard deviation, minimum and maximum, etc.) of observed values and change from baseline values will be presented at each study visit by procedure.

A listing will be provided by procedure which presents all the subjects with an increase or decrease in IOP of more than 10 mmHg at any visit compared to the same eye at baseline.

5.3.7 Problems during Surgery

Surgical problems are collected at operative Visit 00 (Day 0).

Numbers and percentages on operative eye with surgical problems will be presented by procedure. A listing of subjects with surgical problems will be provided by procedure.

5.3.8 IOL Placement

IOL placement data is collected at operative Visit 00 (Day 0).

Numbers and percentages on eye(s) with a change from baseline in IOL position category (Tilted, Decentered) will be presented by procedure. A listing of subjects with IOL position change will be provided by procedure. The listing will include the following variables: procedure, investigator, subject, age, sex, visit, eye and amount of tilting or decentration.

5.3.9 Device Deficiencies

Device deficiencies data is collected at operative Visit 00 (Day 1). A frequency table showing counts and percentages for each device deficiency category will be provided by procedure. A listing of all device deficiencies will be provided by procedure.

5.4 Interim Analysis for Safety

Not Applicable.

6 Sample Size and Power Calculations

Based on previous studies, a sample size of 53 subjects in each procedure group will have a 80% power to detect a mean difference of -7.4 percent-seconds in CDE between the two procedure groups (Centurion® with the 45° Balanced tip minus Infiniti® with the MFK tip) using a two-sample t-test with a one-sided 5% level of significance, assuming a common standard deviation of 15.2.. Assuming a 10% dropout rate, 59 subjects per procedure group (up to 177 in total) will be randomized.

7 References

See protocol Section 17 for details.

8 Revision History

8.1 Revisions for Version 2.0

The following revisions were made to Version 2.0 of the Statistical Analysis Plan to provide additional clarification to the analysis of performance and safety endpoints.

- Analysis of Anterior chamber cells, Anterior chamber flare and Endothelial cell counts were removed from the safety analysis section as it was already covered under the performance analysis section. In addition, some editorial changes were made to the safety endpoints.
- To be consistent with the protocol, changes were made to the reporting of BCDVA data using logMAR instead of number of letters read.
- Additional editorial changes.

8.2 Revisions for Version 3.0

The following revisions were made to Version 3.0 of the Statistical Analysis Plan to correct the calculation for Estimated Incision Leakage and to provide clarification on how endothelial cell density data would be analyzed.

In Section 1.1, the sentences:

[REDACTED]

*BSS Used for Centurion = (Bag Weight after Prime)-(Bag Weight after surgery) – 0.5ml

*BSS Used for Infiniti = (Bottle Weight after prime)-((Bottle weigh after Surgery)

[REDACTED]

were changed to

[REDACTED]

*BSS Used for Centurion = (Bag Weight after Prime) – (Bag Weight after Surgery) – 0.5ml

*BSS Used for Infiniti = (Bottle Weight after prime) – (Bottle Weight after Surgery)

[REDACTED]

In addition, the following sentences were added to Section 4.2:

Up to three specular microscopy images will be taken of the study eye at Visit 0 and Visit 3. The mean of the up to three values for endothelial cell density, coefficient of variation and percent hexagonal cells, rounded to one decimal place, will be used in the analyses.

9 Appendix

Table 11.-1 Schedule of Visits

Activity	Visit 0 (-60 to 0 d)	Visit 00 (0 d)	Visit 1 (1 d)	Visit 2 (7 +/- 2 d)	Visit 3 (90 +/- 14d)
	Unilateral examination				
Informed Consent	X				
Demographics	X				
Medical History	X	X			
Concomitant Medications	X	X	X	X	X
Inclusion/Exclusion	X	X			
Surgery		X			
Problems During Surgery		X			
Other Procedures at Surgery		X			
Lens Information		X			
IOL Placement		X			
Programmable Phacoemulsification Settings			X		
Phacoemulsification Metrics (Including CDE, BSS Fluid Use, [REDACTED])			X		
Visual Acuity (UCDVA & BCDVA)	X			X	X
Intraocular Pressure	X		X	X	X
Specular Microscopy	X				X
[REDACTED]	X		X	X	
Slit Lamp Examination	X		X	X	X
Crystalline Lens Assessment	X				
Anterior chamber cells and flare	X		X	X	X
Dilated Fundus Examination	X				X
Randomization*	X				
Adverse Events (Including Secondary Surgical Intervention)	X	X	X	X	X
Device Deficiencies		X			
Complete Exit Form ¹					X

If a subject exits early, the Visit 3 procedures should be performed at the last available visit, if at all possible.

*Randomization should be completed within 2 working days prior to the date of surgery.

Date/Time (mm/dd/yyyy GMT):	Signed by:	Justification:
